8.4.5 Management of selected naxitamab adverse reactions

8.4.5.1 Management of bronchospasm and hypoxia

Bronchospasm Grade 2

- Reduce naxitamab infusion rate to approximately 50% of previous infusion rate
- Give nebulized beta2-adrenergic receptor agonist
- If the patient stabilizes and recovers (i.e., bronchospasm CTCAE Grade ≤ 1), the infusion rate can be increased to previous rate based on clinical judgement

Bronchospasm with hypoxia CTCAE ≥ 3

- Pause naxitamab infusion
- Give nebulized beta2-adrenergic receptor agonist
- If the response is not satisfactory treat according to local SoC
 - Consider epinephrine inhalation
 - Consider additional IV antihistamine
 - Consider IV corticosteroids
- If the patient stabilizes and recovers from hypoxia (meaning bronchospasm CTCAE Grade ≤ 2), resume infusion at approximately 50% of previous infusion rate. If the patient continues to be stabilized, infusion rate can gradually be increased to infusion rate prior to the event based on clinical judgement
- Please refer to Section 7.12 for treatment discontinuation criteria

8.4.5.2 Management of hypotension

Hypotension Grade 2

- Administer 0.9% saline bolus 10-20 mL/kg IV over 5-15 min

Hypotension Grade 3 without other signs or symptoms

- Decrease naxitamab infusion rate to approximately 50%
- Administer IV 0.9% saline bolus 10-20 mL/kg over 5-15 min. Monitor blood pressure (BP) closely (at least after completion of the bolus and again 15 min later)
 - If the patient remains hypotensive, repeat bolus as described above (maximum a total of 60 mL/kg) and consider additional treatments as described below
 - If the patient stabilizes, consider increasing to the infusion rate prior to the event

Hypotension Grade 3 with other signs or symptoms such as bradycardia, hypoxia, not adequately responding to treatment or Grade 4 hypotension

- Pause naxitamab infusion
- Initiate aggressive fluid resuscitation according to local standard of care (e.g., American College of Critical Care Medicine (ACCC)⁴¹)
- Monitor vital signs closely
- If the patient remains hypotensive, repeat IV 0.9% saline bolus as described above
 - If resolution to CTCAE \leq Grade 2: resume naxitamab infusion at approximately 50% of the previous infusion rate. If the patient has stabilized and the naxitamab infusion is well tolerated increase to the infusion rate prior to the event at the discretion of the investigator

- If the patient remains hypotensive, consider additional treatments as described below
- If the patient is NOT warm and well-perfused **or** do not respond satisfactorily to IV 0.9% saline bolus treatments **or** does respond to IV 0.9% saline bolus but only temporarily, the following should be considered:
 - Give naloxone if the patient is difficult to arouse
 - If naloxone has no effect or based on clinical judgement, consider administration of an inotrope/pressor according to local SoC (e.g., epinephrine IV/intramuscular (IM))
 - If desired effect is achieved and the hypotension is CTCAE \leq Grade 2, consider resuming naxitamab infusion at 50% of the previous infusion rate. If hypotension CTCAE Grade 3 occurs again consider halting naxitamab infusion
 - If the patient continues to be hypotensive and difficult to arouse, stop the current naxitamab infusion permanently and initiate appropriate treatment and observations at the discretion of the investigator (e.g., hospitalization in the intensive care unit)
- Next naxitamab infusion is to be initiated at 50% of the initial infusion rate prior to the event at the discretion of the investigator. Adjustment of the premedication's should be considered

8.4.5.3 Management of hypertension

- Treat all possible causes including pain, urinary retention, allergic reaction, anxiety, and agitation
- Treat hypertension according to local SoC

If hypertension persists at the 90th percentile or higher of BP for age, height, and sex according to National Institutes of Health (NIH)⁴² guideline

- Before naxitamab infusion: The investigator should be informed.
- During naxitamab infusion: Follow the patient closely with additional BP measurements
- After naxitamab infusion: The patient should be followed closely with additional BP measurements and physical examination:
 - During the naxitamab treatment cycle: Additional BP measurements between treatment days i.e., on Days 3, 5, 7 and 9 (on Days 2 and 4 for patients treated with naxitamab+GM-CSF alone (see [Appendix 2](#))
 - After the last dose of naxitamab in a cycle, i.e., on Day 10 (on Day 5 for patients treated with naxitamab + GM-CSF alone, see [Appendix 2](#)):
 - additional BP measurements the following 3 days on Days 11, 12 and 13 (on Days 6, 7 and 8 for patients treated with naxitamab + GM-CSF alone, see [Appendix 2](#))
 - physical examination on Day 13 (Day 8 for patients treated with naxitamab + GM-CSF alone, see [Appendix 2](#))

If hypertension persists at the 99th percentile or higher of BP for age, height, and sex according to NIH⁴² guideline

- Before naxitamab infusion:

- The BP should be treated before infusion can be initiated (see below for details on hypertension algorithm)
- During naxitamab infusion:
 - Treat any pain, anxiety, and/or fluid retention as applicable follow the patient closely with additional BP measurements
 - Consider medical interventions at the discretion of the investigator
- After naxitamab infusion:
 - Start therapy for acute hypertension according to local SoC (e.g., a calcium channel blocker as needed)
 - Admit to inpatient services for monitoring
 - If the patient does respond to anti-hypertensive therapy, an angiotensin-converting enzyme (ACE) inhibitor (e.g., enalapril at starting dose 0.08 mg/kg/dose once daily; max dose 5mg daily) or a calcium antagonist (e.g., amlodipine according to local SoC) may be prescribed prior to future cycles of naxitamab at the discretion of the investigator
 - If the patient has a history of hypertension with naxitamab requiring antihypertensive treatment (e.g., enalapril/amlodipine) on treatment days, consider holding the antihypertensive therapy on Day 2 to avoid potential hypotension
 - If the patient does not respond to anti-hypertensive therapy, consider permanent discontinuation from naxitamab treatment

Posterior reversible encephalopathy syndrome (PRES)

In case of increased risk of PRES (including high BP, headache, seizures, altered consciousness and visual disturbance):

- Admit patient for observation and consider anti-hypertensive therapy
- When BPs are stable < 99th percentile for height according to NIH⁴² the patient can be discharged but should return the next day for follow-up and further treatment of hypertension at the discretion of the investigator
- Please also refer to Section 7.12 for treatment discontinuation criteria

8.4.5.4 Management of infusion-related reactions \geq CTCAE Grade 2, other than hypoxia, bronchospasm, hypotension, and hypertension

- Pause naxitamab infusion
- If resolution to CTCAE Grade \leq 1:
 - Resume naxitamab infusion at 50% of the previous infusion rate and monitor closely at bedside
 - When signs and symptoms resolve, gradually increase infusion rate up to the rate before the event at the investigator's discretion
 - If reaction occurs again, reduce naxitamab to the tolerated infusion rate throughout the remaining time of the infusion
 - At the next naxitamab infusion, the infusion rate should be initiated at the reduced rate. If well tolerated the infusion rate can be gradually increased at the investigator's clinical judgement
- If no resolution of the reaction:

- Consider appropriate treatment at the discretion of the investigator (see Section 8.4)
- If resolution to \leq CTCAE Grade 1, consider resuming naxitamab infusion at 50% of the previous infusion rate as described above
- If no resolution, consider additional treatments and observations, and whether to stop current infusion at the investigator's clinical judgement.
- Please refer to Section 7.12 for discontinuation criteria

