4 EOT visit should take place 6 (up to 10) weeks after last treatment. If treatment is discontinued due to progressive disease (PD), initiation of new anti-NB treatment prohibited as per protocol, withdrawal from the trial or investigator judges it warranted due to medical reasons/non-compliance, the patient should be called for EOT visit as soon as possible and subsequently be followed for safety and new anti-cancer therapy for 6 weeks after last treatment, and herafter continue in the long-term follow-up.

5 Long-term follow-up (FU) evaluations should take place approximately every 4 months until 2 years after End of Treatment. During long-term FU, information on death, PD, serious adverse events (SAEs) ongoing at EOT, new SAEs at least possibly related to naxitamab, new onset of secondary malignancies and autoimmune diseases should be collected. Furthermore, new anti-cancer therapy should be collected as concomitant medication. (see Section 9.1).

6 Screening imaging and BM examination must be obtained at least 10 calendar days after any prior anti-cancer treatment.

7 Only applicable for D-3 to 0 in cycle 1.

8 Height, weight, physical examination, clinical laboratory assessments, anti-drug antibodies (ADA) and performance test must be performed prior to dosing in each cycle; prior to day (D)1 or at D1.

9 Serum pregnancy test must be done on D-3 prior to gabapentin administration for women of childbearing potential

10 Should only be performed at D15 during C1.

11 Bilateral aspirates and bone marrow (BM) biopsies (2+2), performed at screening and after C2, C4, C8, C13, and EOT. In addition, for patients who achieve a first CR or PR after C4 or a first CR or PR after C8 a confirmatory response assessment should be performed within 4-6 weeks after detection of the overall response. Samples for RTqPCR should be taken at Screening and after C2 and C4. See section section 9.1.2

12 Imaging schedule follows timing of BM biopsies (see #11 above). For a Fluorodeoxyglucose Positron Emission Tomography/ Computed Tomography (FDG PET/CT) scan, the patient must be in fasting state for at least 4 hours prior to the scan. If the patient is not fasting serum glucose determination must be performed prior to the administration of FDG. Please refer to the imaging acquisition guideline for more details.

13 Not to be performed at EOT if the patient discontinue treatment due to PD, provided that PD is documented by scan and/or biopsy. See section [section 9.1.2](#)

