In terms of safety across Trials 12-230 and 201, naxitamab was found to be generally well tolerated with a manageable safety profile. The acute toxicities/infusion related adverse events (AEs) included mainly Common Terminology Criteria for Adverse Events (CTCAE) Grade 1-2 events. Treatment-Emergent AEs (TEAE) occurring in \geq 50% of patients in at least one of the 2 trials included hypotension, urticaria, abdominal pain, pyrexia, tachycardia, bronchospasm, cough, flushing, nausea, vomiting, decreased appetite, diarrhoea, pain in extremity and pruritus. Across the 2 trials, TEAEs of CTCAE grade 3 or higher were reported in █████ to 92% of patients. TEAEs of grade 3 or higher reported in \geq 10% of the patients in at least one of the trials were pain, hypotension, urticaria, bronchospasm, stridor, depressed level of consciousness and neutropenia. The acute toxicities/infusion related AEs were generally managed by pre-medications (opioids, corticosteroids, antipyretics, and antihistamines) along with concomitant administration of normal saline, opioids, nebulized beta-2 agonists, and oxygen as applicable during the naxitamab infusion. █████, 2 events of posterior reversible encephalopathy syndrome (PRES) (CTCAE grade 3) with onset 2 and 7 days after the last dose in Cycle 1 were reported in connection with hypertension in █████. No new events of PRES have been reported after the implementation of mitigations for hypertension. One (1) case of transverse myelitis (CTCAE Grade 3) has been reported in a single patient treated under single patient use █████. The patient was treated with high dose methylprednisolone and recovered subsequently. The event is seen as a possible class effect with anti-GD2 antibodies.

In trials 12-230 and 201, 23.1% and 8.3%, respectively, developed ADAs. █████

██████████ As only 2 subjects developed ADA in 201 at the time of the interim analysis, very limited information was available regarding efficacy and safety in this subgroup.

Based on the above data, naxitamab (Danyelza[®]) received accelerated regulatory approval on 25Nov 2020 by the FDA in the US for the treatment in combination with

GM-CSF of patients \geq 1 year of age with relapsed or refractory high-risk NB in the bone or BM demonstrating a PR, minor response (MR), or stable disease (SD) to prior therapy for NB.

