8.1.3 Treatment delays and missed dosing

Minor adjustment of the treatment schedule due to medical circumstances (e.g., infection) at the discretion of the investigator or non-medical circumstances (e.g., public holidays) is allowed.

It is allowed to postpone the start of a new cycle due to IT toxicity for up to 21 days after the planned subsequent cycle start date (i.e., < 3-weeks delay in start of next cycle) (please see treatment discontinuation criteria Section [7.12](#)).

If a naxitamab dose is missed, administer the missed dose on Day 12. In that case, treatment with GM-CSF at 250 µg/m²/day should be continued until Day 12 (i.e., treatment from Day 6 to Day 12). Please refer to [Appendix 2](#) if the patient has discontinued IT treatment due to toxicity.

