9.2.2 Vital Signs

Vital sign measurements must include heart rate, respiratory rate, body temperature and BP. Additionally, peripheral oxygen saturation (SpO₂) must be measured when clinically indicated. Temperature must be measured by using the same method (e.g., ear thermometer) each time. Vital signs must be assessed at screening and in connection with each treatment cycle as outlined below:

On Days 1, 3 and 5 prior to administration of temozolomide.

On naxitamab in fusion days (Days 2, 4, 8 and 10)

- Prior to administration of temozolomide (Days 2 and 4)
- Prior to pre-medication (e.g., hydromorphone or morphine)
- Prior to start of naxitamab infusion
- ~15 min after start of naxitamab infusion
- ~30 min after start of naxitamab infusion
- Prior to each hydromorphone or morphine IV therapy as feasible (no temperature)
- At completion of naxitamab infusion including flush (no temperature)

- ~15 min after completion of the flush (no temperature)
- Every hour while patient is recovering in the outpatient clinic

Furthermore, vital signs must be assessed at EOT and as clinically indicated. The latter includes when a vital sign parameter is part of an AE on an infusion day.

Please refer to [Appendix 2](#) for patients who have discontinued IT treatment due to toxicity.

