If a naxitamab dose is missed, administer the missed dose the following week, but the 3 infusions of naxitamab must be administered within a period of maximum 10 days. If a patient is treated on a modified schedule, the GM-CSF dosage will be the same as the standard on days -4 to 0, but GM-CSF will be administered at 500 μ g/m²/day on the day of the first infusion of naxitamab, on the day before and on the day of the second infusion of naxitamab, and on the day before and on the day of the third infusion of naxitamab. The modified schedule ensures that the same total dosage of GM-CSF is administered in the standard and in the modified schedules.

Laboratory assessments:

Laboratory tests should be performed as described in the table below and as clinically indicated.

Table 14 Protocol required laboratory assessments for patient treated with naxitamab + GM-CSF alone

Timing of Laboratory assessments	Parameters
All cycles*: Prior to dosing D-4, D1, D3, D5 EOT * If modified naxitamab dosing due to missed dose (ie naxitamab missed dose to be administered within the first 10 days of a cycle) check hematology parameters on day of last naxitamab administration in the cycle prior to administration of GM-CSF	Hematology 
 • Hemoglobin • Hematocrit • White blood cells (WBC) • Lymphocytes (absolute) • Neutrophils (absolute) • Eosinophils (absolute) • Basophils (absolute) • Monocytes (absolute) • Platelet count
All cycles: prior to dosing D1, D3, D5 EOT	Liver and kidney function blood tests 
 • ALT • AST • Alkaline phosphatase • Total bilirubin • LDH • BUN • Creatinine • Albumin (only prior to each cycle)
All cycles: prior to dosing D1, D3, D5 EOT	Serum electrolytes 
 • Sodium • Potassium
Prior to each cycle	Urine analysis (dipstick) 
 • Protein • Glucose • Leucocytes
Prior to each cycle EOT	Pregnancy test, if applicable Serum pregnancy test for WOCBP see 9.2.8 for further information
ADA Prior dosing in each cycle EOT	
 • Anti-naxitamab antibodies • Naxitamab AB (neutralizing effect)

The complete blood count (CBC) and differential counts should be repeated on sequential days during all treatment cycles if ANC is $> 20 \times 10^9/L$ or WBC $> 50 \times 10^9/L$ on the previous day.

Vital signs

- Prior to pre-medication (e.g., hydromorphone or morphine)
- Prior to start of naxitamab infusion

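### The fixed blood-pressure follow-up days in section 8.4.5.3 fit neither the make-up-dose rules nor the 7-day PRES onset cited in section 4.3.2

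*Combined protocol and SAP*

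**What the plan says.** Section 8.4.5.3 applies this step under the condition "If hypertension persists at the 90th percentile or higher of BP for age, height, and sex". After the last naxitamab dose of the cycle, which it places on Day 10, it requires "additional BP measurements the following 3 days on Days 11, 12 and 13" and a physical examination on Day 13. For the regimen without irinotecan and temozolomide the last dose is placed on Day 5, the readings fall "on Days 6, 7 and 8 for patients treated with naxitamab + GM-CSF alone", and the examination is on Day 8.

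The last dose can come later than this. Section 8.1.3 says: "If a naxitamab dose is missed, administer the missed dose on Day 12". Appendix 2 moves a missed dose to the following week, provided that "the 3 infusions of naxitamab must be administered within a period of maximum 10 days".

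Section 4.3.2 reports two Grade 3 PRES events "with onset 2 and 7 days after the last dose in Cycle 1 were reported in connection with hypertension". It adds that none has been reported since mitigations for hypertension were introduced, without saying what those mitigations were.

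For the four-drug regimen (HITS), section 9.2.2 schedules vital signs at screening, "On Days 1, 3 and 5 prior to administration of temozolomide", on the naxitamab infusion days (2, 4, 8 and 10), at end of treatment and when clinically indicated. Table 1 also has a Day 15 contact. Its footnote, "Should only be performed at D15 during C1", is attached to laboratory tests, adverse events and concomitant medication.

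**The concern.** The rule in section 8.4.5.3 has two parts that can disagree: a number of days counted from the last dose, and a list of calendar days. They agree only when dosing runs on the standard schedule. After a make-up dose, a site that follows the printed days takes fewer readings after the last dose than the rule's own words require, or none.

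Separately, the protocol's own safety background has one of two PRES events starting later than the last scheduled reading, and no reason is given for stopping at 3 days. PRES leads to discontinuation of all investigational products (section 7.12), and high blood pressure is among the risk signs that section 8.4.5.3 lists for it. Sites therefore need a schedule with only one reading, and the length of the window should be explained against the cited onset times.

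**Working it through.** **Inputs.** Printed readings and examinations: section 8.4.5.3. Make-up doses: section 8.1.3 and Appendix 2. PRES lags of 2 and 7 days: section 4.3.2. Cycle lengths of 21 and 28 days: section 7.2.1. Scheduled vital signs: section 9.2.2, Table 1 and Table 12.

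**Step 1. Printed days against the last dose.** Offset = printed day − day of last dose. For Appendix 2, I take the first infusion as Day 1 and count it as the first of the 10 days, so the latest dose is on Day 1 + 10 − 1 = Day 10. The note in Table 14, which refers to the first 10 days of a cycle, agrees.

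| Case | Last dose | Printed days | Offsets | Readings after last dose |
|---|---|---|---|---|
| HITS, standard | Day 10 | 11, 12, 13 | +1, +2, +3 | 3 |
| HITS, make-up dose | Day 12 | 11, 12, 13 | −1, 0, +1 | 1 |
| Naxitamab + GM-CSF alone, standard | Day 5 | 6, 7, 8 | +1, +2, +3 | 3 |
| Naxitamab + GM-CSF alone, latest make-up dose | Day 10 | 6, 7, 8 | −4, −3, −2 | 0 |

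The standard rows reproduce the plan's 3 days. With a Day 12 dose, counting three days from the dose gives Days 13, 14 and 15; only Day 13 is printed.

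The examination moves in the same way. In HITS it goes from 13 − 10 = +3 to 13 − 12 = +1. Under Appendix 2 it goes from 8 − 5 = +3 to 8 − 10 = −2, so it could come two days before the last dose.

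**Step 2. Was other timing adapted?** Yes. Table 9 adds Day 10 hematology when a dose moves to Day 12, and Table 14 asks for hematology on the day of the last naxitamab dose when the schedule is modified. Section 8.4.5.3 has no matching note.

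**Step 3. The window against the cited PRES onsets.** Onset day = last dose + lag.

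- HITS: 10 + 2 = Day 12, inside the window; 10 + 7 = Day 17, and 17 − 13 = 4 days after the last reading.
- Naxitamab + GM-CSF alone: 5 + 2 = Day 7, inside; 5 + 7 = Day 12, and 12 − 8 = 4 days after the last reading.

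**Step 4. What else is scheduled.** In HITS the next Day 1 is Day 22 if the cycle starts on time. No blood pressure is scheduled on Days 14 to 21, which is 8 of 21 days. Day 15 is 15 − 10 = +5, so a reading there would still come 17 − 15 = 2 days before a 7-day onset. That contact exists only in Cycle 1 of HITS. The column alignment of Table 1 is unreliable in the text copy, so the absence of vital signs at Day 15 rests on section 9.2.2. The row's ten marks (screening, Days 1 to 5, 8, 10, next cycles, end of treatment) agree with it.

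**The case against.** On the make-up doses, the governing phrase counts from the last dose, and the printed days can be read as describing the standard schedule only. A careful site would then shift them. That is a fair reading, but the text does not say so, and the laboratory tables show that the authors wrote out such shifts where they wanted them.

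On PRES, the case against is stronger. A reader might infer that the 3-day window would have missed the second patient. The documents do not support this: section 4.3.2 gives the onset of PRES, not of hypertension, and that patient's pressure may already have been high within 3 days. The source of the events is partly blacked out. The earlier trials described there gave naxitamab on Days 1, 3 and 5, which matches Appendix 2 but not HITS, and no PRES has been reported since the mitigations.

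A reader might also infer that later hypertension would be found only through symptoms. For flagged patients this is not established. There is the Day 13 (Day 8) examination, which covers the neurologic system and altered vision (section 9.2.1). There is also admission at or above the 99th percentile, the PRES-risk rule with its five listed signs, vital signs when clinically indicated, and follow-up of adverse events of special interest until resolved, chronic or stable (section 10.8). What stands is that none of these fixes a blood-pressure reading after Day 13 (Day 8) in that cycle.

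Finally, a reader might infer that the count of hypertension events of special interest is biased downward. Section 10.4 counts persistent hypertension once it requires the additional monitoring, so the length of that monitoring does not decide whether a flagged patient is counted. The other criterion is the need for antihypertensive therapy. New late hypertension could go unread, but no figure in the documents shows a bias or its size.

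**Conclusion.** The point holds as an internal inconsistency and an unexplained choice. The firmer part is the day numbering: after a make-up dose, one of three printed readings remains in HITS and none in the latest Appendix 2 case, where the examination can also precede the last dose. This needs no clinical judgment, only the assumption that the ten-day period starts on Day 1.

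The second part is narrower. One of two cited PRES onsets lies 4 days beyond the scheduled readings, and the protocol does not say why 3 days is enough. This rests on two events and on carrying the lag from last dose over to the present regimens. It does not show that the window is inadequate. The point is safety-relevant and cheap to settle in the next amendment; it does not touch the primary endpoint.

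**What to change.** Reconcile the printed days in section 8.4.5.3, for both the readings and the examination, with that section's own count from the last dose and with the make-up-dose rules in section 8.1.3 and Appendix 2.

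Reconcile the scheduled blood-pressure follow-up with the 7-day onset in section 4.3.2, or state why the present window is sufficient, including what the mitigations mentioned there were. As part of this, the sponsor should say whether blood pressure belongs at the existing Cycle 1 Day 15 contact, bearing in mind that this alone would not reach a 7-day onset and would not apply to Appendix 2. The sponsor's clinical team sets the schedule; no particular window is proposed here.

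The cost is a few lines in the next amendment. Any added readings would depend on what the clinical team decides.

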8.1.2.3 Naxitamab

On days when co-administered with GM-CSF, naxitamab infusion is started ≥ 60 min after GM-CSF.

On days when co-administered with IT (i.e., Days 2 and 4), it is recommended to start naxitamab infusion at least 1 hour after irinotecan administration to allow for preparations and administration of pre-medications.

Naxitamab should be infused IV at 2.25 mg/kg/day on Days 2, 4, 8 and 10 for a total dose of 9 mg/kg per cycle (Please refer to Appendix 2 for details on naxitamab treatment if the patient has discontinued IT treatment due to toxicity). Administration of naxitamab should be adjusted according to Section 8.4.5, if selected naxitamab adverse reactions are observed. If any events occur fulfilling a general discontinuation criterion the patient must be withdrawn from all treatments immediately and enter long-term FU, see Section 7.12.

At Cycle 1 Day 2 (C1D2):

Naxitamab should be infused over approximately 60 min.

All subsequent naxitamab infusions:

Naxitamab should be infused over approximately 30 min.

Special circumstances

The infusion may be given over approximately 60 min. at Day 2 of any cycle at the investigator's discretion if:

- The patient during C1D2 experienced naxitamab related hypotension:
 - Grade 4 **or**
 - Grade 3 not adequately responding to intervention
- At the investigator's discretion due to severe infusion related adverse drug reactions not adequately responding to interventions

The 60/30 min infusion time is a minimum infusion time. If infusion pause or infusion rate reduction is required due to infusion related AE (see Section [8.4.5](#)) the infusion time will become longer.

Naxitamab treatment in an out-patient setting is defined as a naxitamab infusion performed in the ambulatory setting.

In-patient treatment (i.e. requiring hospitalization) includes both short term admissions and admissions requiring overnight stay.

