8.4.1 Pre-medications Prior to Naxitamab Infusions

Pre-medication is needed to mitigate expected AEs with naxitamab. These include pain, infusion-related reactions, hypotension, allergic reactions, nausea/vomiting and potentially anxiety.

Infusion with naxitamab is associated with pain that may be severe. The pain may involve the abdomen, lower back, chest, legs and arms. The duration may vary but, for most patients, the pain lasts for a couple of hours, and tends to be worst during the naxitamab infusion, subsiding approximately 15 min after end of infusion. Due to the pain, patients may “hold their breath”. A marked variation in the naxitamab-associated pain may be observed from infusion to infusion, and hence the recommended opioid dosages below are applicable only to the first infusion. Opioid pre-medications for mitigation of pain during subsequent infusions of naxitamab and pain medications after completion of the naxitamab infusion should be adjusted at the discretion of the investigator.

All medications (including opioid usage) should be captured on the concomitant medication eCRF.

At home

To reduce the risk of pain, gabapentin should be administered from Day -3 to Day 12 of each cycle according to local SoC (e.g., dose of 5 to 10 mg/kg with a max dose of 600 mg).

It is recommended to titrate to the final effective dose during the first 3 days of treatment:

Day -3: Once daily; Day -2: Twice daily; Day -1 and until Day 10: 3 daily doses (please refer to [Appendix 2](#) if the patient has discontinued IT treatment due to toxicity).

After completion of the naxitamab treatment (i.e. Day 10), it is recommended to taper off the gabapentin treatment: Day 11: Twice daily; Day 12: Once daily. If nerve pain lingers, the patient may continue gabapentin on twice daily dosing for up to a week post naxitamab treatment before further weaning.

At hospital

- Saline solution 0.9% (to reduce risk of severe hypotension)
 - Patients should be preloaded with saline 0.9% infusion 10mL/kg over 1 hour just prior to the start of all naxitamab infusions
- Opioids
 - Per os (PO) opioids are preferred over IV to diminish IV related side effect such as hypotension, respiratory depression, and/or decreased responsiveness
 - Oxycodone 0.1 – 0.2 mg/kg with a max dose of 5 mg PO (45 – 60 min before naxitamab infusion) **or** equivalent dose of PO opioids **or**

- In cases where PO administration is not feasible (15 min before naxitamab infusion):

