Naxitamab should be infused IV at 3 mg/kg/day on Days 1, 3, and 5 for a total dose of 9 mg/kg per cycle. Administration of naxitamab should be adjusted according to Section 8.4.5 if selected naxitamab adverse reactions are observed. If any events occur fulfilling a general

discontinuation criterion the patient must be withdrawn from naxitamab and GM-CSF treatment immediately and enter long-term follow-up, see Section [7.12](#).

Naxitamab should be infused over approx. 30 min.

Special circumstances:

The infusion may be given over approximately 60 min. at Day 1 of any cycle at the investigator's discretion if:

- The patient during the C1D2 infusion (HITS regimen) experienced naxitamab related hypotension:
 - CTCAE Grade 4 **or**
 - Grade 3 not adequately responding
- At the investigators discretion due to severe infusion related adverse drug reactions not adequately responding to interventions

The 60/30 min infusion time is a minimum infusion time. If infusion pause or infusion rate reduction is required due to infusion related AE (see Section [8.4.5](#)) the infusion time will become longer.

Table 13 Treatment with naxitamab + GM-CSF alone

Treatment days in cycles of 28 days	-4 to 0	1	2	3	4	5	6+7	11-28
Premedication (analgesics and/or antihistamines) (8.4.1)	X	X	X	X	X	X	X	
GM-CSF 250 μ g/m ² /day s.c (8.4.6) ¹	X							
GM-CSF 500 μ g/m ² /day s.c (8.4.6) ¹		X	X	X	X	X		
Naxitamab 3 mg/kg/day IV (9mg/kg/cycle) ¹ (8.1.2.3) ¹		X		X		X		

¹ Patients achieving a CR or PR should receive 8 naxitamab cycles or 5 additional naxitamab cycles following the OR, whichever provides the longest treatment with naxitamab. Patients who have achieved a MR or SD at completion of the 8 cycles may receive naxitamab + GM-CSF consolidation treatment for 5 cycles administered at every 8 weeks. The total number naxitamab cycles to be administered includes the treatment cycles administered in the HITS regimen

Missed dosing

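### The option in Section 8.4.5.3 to hold antihypertensives on Day 2 is not converted for naxitamab + GM-CSF alone, where Day 2 is not an infusion day

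*Combined protocol and SAP*

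**What the plan says.** Section 8.4.5.3 governs hypertension in both regimens. Appendix 2 has no hypertension rules of its own and sends patients on naxitamab + GM-CSF alone to Section 8.4.5.

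In the part on pressures persisting at the 90th percentile or above, each numbered day has a counterpart for the alone regimen. The extra blood pressure checks between treatment days are "on Days 3, 5, 7 and 9 (on Days 2 and 4 for patients treated with naxitamab+GM-CSF alone", and the follow-up visit is a "physical examination on Day 13 (Day 8 for patients treated with naxitamab + GM-CSF alone".

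The part on the 99th percentile ends with advice for patients who have already needed antihypertensives on naxitamab treatment days: "consider holding the antihypertensive therapy on Day 2 to avoid potential hypotension". No counterpart day follows. One drug the section offers for use before later cycles is "enalapril at starting dose 0.08 mg/kg/dose once daily; max dose 5mg daily".

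On the infusion schedule, Section 8.1.2.3 puts naxitamab on Days 2, 4, 8 and 10 of a HITS cycle. For the alone regimen, Appendix 2 states: "Naxitamab should be infused IV at 3 mg/kg/day on Days 1, 3, and 5 for a total dose of 9 mg/kg per cycle".

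**The concern.** The hold is meant to prevent hypotension, so it should coincide with an infusion. In HITS it does, because Day 2 opens the naxitamab course. In the alone regimen the printed day falls between the first and second infusions.

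Two consequences follow if the text is taken literally:

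- No hold is suggested before the first infusion, which is the situation the HITS rule addresses.
- A patient on a once-daily drug such as enalapril could miss a dose on Day 2. If that patient's hypertension persists, the same section asks for extra pressure checks on that day.

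For a drug given only on infusion days, the advice simply has no effect in this regimen.

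Hypotension is a recognised naxitamab risk. Section 4.3.2 lists it among the events of Grade 3 or higher seen in at least 10% of patients in at least one earlier trial, and Section 10.4 makes Grade 3 hypotension an event of special interest. Each infusion in the alone regimen is also larger: 3.0 against 2.25 mg/kg, and 3.0 / 2.25 = 1.33, or one third more.

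**Working it through.** No statistical figure is involved. The check sets the day references against the infusion schedules.

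**Infusion days**

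- HITS (Section 8.1.2.3, Table 4): {2, 4, 8, 10}; first infusion on Day 2.
- Naxitamab + GM-CSF alone (Appendix 2 text, Table 13): {1, 3, 5}; first infusion on Day 1.
- Day 2 belongs to the first set and not to the second. GM-CSF is given on Day 2 of the alone regimen, but naxitamab is not.

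**Numbered-day instructions in Section 8.4.5.3**

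| Instruction | HITS | Alone | Converted? |
|---|---|---|---|
| Extra BP checks between treatment days | 3, 5, 7, 9 | 2, 4 | Yes |
| Last naxitamab dose of the cycle | 10 | 5 | Yes |
| BP checks after the last dose | 11, 12, 13 | 6, 7, 8 | Yes |
| Physical examination | 13 | 8 | Yes |
| Optional antihypertensive hold | 2 | none given | No |

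Four of five are converted. The first row also shows that the section itself treats Day 2 of the alone regimen as a day between treatments.

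**Nearest parallel rule**

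The protocol has one other option tied to Day 2, the slower infusion after poorly tolerated hypotension or a severe infusion reaction.

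- Section 8.1.2.3, HITS: "The infusion may be given over approximately 60 min. at Day 2 of any cycle".
- Appendix 2, alone regimen: "The infusion may be given over approximately 60 min. at Day 1 of any cycle".

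Here the protocol maps Day 2 in HITS to Day 1 in the alone regimen, that is, first infusion to first infusion. The same mapping applied to the hold gives Day 1.

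**Whether another passage supplies the day**

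The alone-regimen material in Appendix 2 (flowchart, pre-medication, dosing, missed doses, laboratory tests, vital signs) has no rule on holding antihypertensives. The gap is not filled elsewhere.

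**The case against.** The textual gap is not in dispute. The case on the other side concerns its importance and the remedy.

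- **The literal reading is strained.** The bullet speaks of antihypertensives needed on treatment days and states its purpose. A careful investigator would see that Day 2 is not a treatment day in the alone regimen and would either ignore the bullet or infer Day 1. This stands in part: many would do so. But the section gives the alternative day everywhere else, so its absence can be read as Day 2 applying to both regimens. The bullet also names enalapril, whose example dose is once daily.
- **The advice is optional and other protection remains.** It only asks the investigator to consider a hold. Section 8.4.1 requires fluid beforehand: "Patients should be preloaded with saline 0.9% infusion 10mL/kg over 1 hour just prior to the start of all naxitamab infusions". Vital signs around each infusion and the graded hypotension algorithm in Section 8.4.5.2 also apply. This stands, and it is why the point ranks low.
- **The count overstates the pattern.** All four converted references sit in the 90th-percentile part, and three of them concern the period from the last dose onwards. The hold is the only day reference in the 99th-percentile part. This is accurate, so four of five describes the text and does not measure harm.
- **Naming Day 1 is a clinical choice.** Withholding treatment from patients with known hypertension bears on the opposing risk of posterior reversible encephalopathy syndrome. Section 4.3.2 reports two Grade 3 cases in connection with hypertension, and Section 7.12 makes the syndrome a reason to stop all trial drugs. The risk is real, but the protocol already accepts the same trade-off at the first HITS infusion, and the wording would stay optional.

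**Conclusion.** The concern holds. The hold advice names a day that does not serve its stated purpose in the naxitamab + GM-CSF alone regimen, and nothing in Appendix 2 corrects it. Reading Day 2 as the first infusion of the cycle is an inference, since the protocol does not say why that day was chosen. It rests on the HITS schedule and on the Day 2 to Day 1 conversion of the 60-minute option.

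The point is minor. It reaches only patients who stop irinotecan and temozolomide for toxicity, continue naxitamab + GM-CSF, and have had naxitamab hypertension that needed treatment. The documents give no count for that group, so no frequency can be attached. There is no effect on eligibility, endpoints, sample size, power or the primary analysis.

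**What to change.** In the hold bullet of Section 8.4.5.3, insert directly after the words Day 2: *(Day 1 under naxitamab + GM-CSF alone; see Appendix 2)*. This follows the style of the section's other conversions and agrees with the Day 1 rule that Appendix 2 already has for the slower infusion. The medical lead should confirm Day 1 as the intended day when the text is amended.

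The cost is one parenthesis, which can go into the next amendment. No change is needed to data collection or analysis.
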